#### **8.4.2 Method of Detecting AEs, SAEs, and Other Reportable Safety Events**

Care will be taken not to introduce bias when detecting AEs and/or SAEs and other reportable safety events. Open-ended and nonleading verbal questioning of the participant is the preferred method to inquire about AE occurrence.

#### **8.4.3 Follow-up of AE, SAE, and Other Reportable Safety Event Information**

After the initial AE/SAE report, the investigator is required to proactively follow each participant at subsequent visits/contacts. All AEs, SAEs, and other reportable safety events including pregnancy and exposure during breastfeeding, events of clinical interest (ECIs), cancer, and overdose will be followed until resolution, stabilization, until the event is otherwise explained, or the participant is lost to follow-up (as defined in Section 7.3). In addition, the investigator will make every attempt to follow all nonserious AEs that occur in randomized participants for outcome. Further information on follow-up procedures is given in Appendix 3.

#### **8.4.4 Regulatory Reporting Requirements for SAE**

Prompt notification (within 24 hours) by the investigator to the Sponsor of SAE is essential so that legal obligations and ethical responsibilities towards the safety of participants and the safety of a study intervention under clinical investigation are met.

The Sponsor has a legal responsibility to notify both the local regulatory authority and other regulatory agencies about the safety of a study intervention under clinical investigation. The Sponsor will comply with country-specific regulatory requirements and global laws and regulations relating to safety reporting to regulatory authorities, IRB/IECs, and investigators.

Investigator safety reports must be prepared for suspected unexpected serious adverse reactions (SUSARs) according to local regulatory requirements and Sponsor policy and forwarded to investigators as necessary.

An investigator who receives an investigator safety report describing an SAE or other specific safety information (eg, summary or listing of SAE) from the Sponsor will file it along with the IB and will notify the IRB/IEC, if appropriate according to local requirements.

#### **8.4.5 Pregnancy and Exposure During Breastfeeding**

Although pregnancy and infant exposure during breastfeeding are not considered AEs, any pregnancy or infant exposure during breastfeeding in a participant (spontaneously reported to the investigator or their designee) that occurs during the study are reportable to the Sponsor.

All reported pregnancies must be followed to the completion/termination of the pregnancy. Pregnancy outcomes of spontaneous abortion, missed abortion, benign hydatidiform mole, blighted ovum, fetal death, intrauterine death, miscarriage, and stillbirth must be reported as serious events (Important Medical Events). If the pregnancy continues to term, the outcome (health of infant) must also be reported.

#### **8.4.6 Disease-related Events and/or Disease-related Outcomes Not Qualifying as AEs or SAEs**

Efficacy endpoints as outlined in this section will not be reported to the Sponsor, as described in Section 8.4.1.

Specifically, the suspected/actual events covered in this exception include any event that is progression of the cancer under study.

The Sponsor will monitor unblinded aggregated efficacy endpoint events and safety data to ensure the safety of the participants in the study.

#### **8.4.7 Events of Clinical Interest (ECIs)**

Selected nonserious and SAEs are also known as ECIs and must be reported to the Sponsor.

Events of clinical interest for this study include:

1. An overdose of pembrolizumab, as defined in Section 8.5, that is not associated with clinical symptoms or abnormal laboratory results.
2. Any dose over the prescribed dose of lenvatinib associated with an AE.
3. An elevated AST or ALT lab value that is greater than or equal to 3X the upper limit of normal and an elevated total bilirubin lab value that is greater than or equal to 2X the upper limit of normal and, at the same time, an alkaline phosphatase lab value that is less than 2X the upper limit of normal, as determined by way of protocol-specified laboratory testing or unscheduled laboratory testing.\*

\*Note: These criteria are based upon available regulatory guidance documents. The purpose of the criteria is to specify a threshold of abnormal hepatic tests that may require an additional evaluation for an underlying etiology. The study site guidance for assessment and follow-up of these criteria can be found in the Investigator Study File Binder (or equivalent).

#### **8.5 Treatment of Overdose**

**NOTE: After amendment 007-06, lenvatinib and matching placebo were discontinued. This section was left unchanged for reference.**

For purposes of this study, an overdose will be defined as any dose exceeding the prescribed dose as follows:

- Pembrolizumab:  $\geq 5$  times the protocol-specified dose.
- Lenvatinib: any dose above the protocol-specified dose if associated with an adverse event.

There is no specific antidote for an overdose of lenvatinib. Due to its high degree of plasma protein binding, lenvatinib is not expected to be dialyzable. Adverse reactions in patients receiving single doses of lenvatinib as high as 40 mg were similar to those in clinical studies at the recommended dose for differentiated thyroid cancer and RCC.

No specific information is available on the treatment of overdose of pembrolizumab or lenvatinib. In the event of overdose, the participant should be observed closely for signs of toxicity. Appropriate supportive treatment should be provided if clinically indicated.

All reports of pembrolizumab overdose with and without an AE and all reports of lenvatinib overdose with an AE must be reported by the investigator within 24 hours to the Sponsor either by electronic media or paper.

Reports of pembrolizumab overdose without any associated clinical symptoms or abnormal laboratory results, should be reported using the terminology “accidental or intentional overdose without adverse effect.”

## **8.6 Pharmacokinetics**

As of Protocol Amendment 05, the Sponsor has determined that there is sufficient pembrolizumab/lenvatinib PK data in NSCLC participants. Consequently, no further PK samples for pembrolizumab and lenvatinib or ADA samples for pembrolizumab will be collected.

## **8.7 Pharmacodynamics**

Pharmacodynamic parameters will not be evaluated in this study.

## **8.8 Planned Genetic Analysis Sample Collection**

Samples are to be collected for planned analysis of associations between genetic variants in germline/tumor DNA and drug response. If a documented law or regulation prohibits (or local IRB/IEC does not approve) sample collection for these purposes, then such samples are not be collected at the corresponding sites.

## **8.9 CCI**

[REDACTED]

[REDACTED]

[REDACTED]

[REDACTED]

## 8.10 Medical Resource Utilization and Health Economics

All-cause hospitalizations and emergency room visits must be reported in the eCRF, from the time of treatment randomization through 90 days after cessation of study intervention, or 30 days after cessation of study intervention, if the participant initiates new anticancer therapy, whichever is earlier.

## 8.11 Visit Requirements

**NOTE: As of Amendment 007-06, the Second-course Treatment Phase has been removed from the study. The following subsections have been updated accordingly.**

Visit requirements are outlined in the SoA (Section 1.3). Specific procedure-related details are provided in Section 8.

Unscheduled visits are permitted at any time during the course of the study.

### 8.11.1 Screening

Documented informed consent must be provided before performing any protocol-specific procedure. Results of a test performed before the participant signs the ICF as part of routine clinical management are acceptable in lieu of a screening test if performed within the specified time frame. Screening procedures are to be completed within 28 days before the first dose of study intervention except for the following:

- Laboratory tests are to be performed per the SoA (Section 1.3).
- Evaluation of ECOG is to be performed at screening, within 7 days before Cycle 1 but before randomization.
- For WOCBP, a urine or serum pregnancy test will be performed within 24 hours before the first dose of study intervention. If urine pregnancy results cannot be confirmed as negative, a serum pregnancy test will be required (performed by the local study site laboratory).

Participants may be rescreened after initially failing to meet the inclusion/exclusion criteria. Results from assessments during the initial screening period are acceptable in lieu of a repeat screening test if performed within the specified time frame and the corresponding inclusion/exclusion criteria are met. Participants who are rescreened will retain their original screening number.

### 8.11.2 Initial Treatment Phase

Visit requirements are outlined in the SoA (Section 1.3). Specific procedure-related details are provided in Section 8.1.

### **8.11.3 Second-course Treatment Phase**

**NOTE: As of Amendment 007-06, the Second-course Treatment Phase has been removed from the study.**

### **8.11.4 Discontinued Participants Continuing to be Monitored in the Study**

The Discontinuation Visit should occur at the time study intervention is discontinued for any reason. If the Discontinuation Visit occurs 30 days from the last dose of study intervention, at the time of the mandatory Safety Follow-up Visit, the Discontinuation Visit procedures and any additional safety follow-up procedures should be performed.

Visit requirements are outlined in the SoA. Additional details regarding participant withdrawal and discontinuation are presented in Section 8.1.9.

### **8.11.5 Poststudy**

#### **8.11.5.1 Safety Follow-up Visit**

The mandatory Safety Follow-up Visits should be conducted approximately 30 days after the last dose of study intervention or before the initiation of a new anticancer treatment, whichever comes first.

#### **8.11.5.2 Efficacy Follow-up Visits**

**NOTE: After amendment 007-06, imaging obtained on study will be submitted to the imaging vendor but these will not be assessed, verification of PD is no longer needed before treatment discontinuation, and posttreatment imaging is no longer required.**

Participants who complete the protocol-required cycles of study intervention or who discontinue study intervention for a reason other than PD will move into Efficacy Follow-up Phase and should be assessed as outlined in the SoA (Section 1.3) to monitor disease status. Every effort should be made to collect information regarding disease status until the start of new anticancer therapy, PD, death, or end of study. Information regarding poststudy anticancer treatment will be collected if new treatment is initiated. Participants who completed all efficacy assessments and/or will not have further efficacy assessments must enter Survival Follow-up Phase.

#### **8.11.5.3 Survival Follow-up Assessments**

Participants who experience confirmed PD or start a new anticancer therapy will move into the Survival Follow-Up Phase and should be contacted by telephone approximately every 12 weeks (or more often as required) to assess survival status until death, withdrawal of consent, or the end of the study, whichever occurs first. Participants may be contacted for survival status at any time during the course of the study.

## 9 STATISTICAL ANALYSIS PLAN

**NOTE: Data from an interim safety and futility eDMC for LEAP-007 (data cutoff: 19-MAY-2021) indicated that the study met the prespecified nonbinding futility criteria for OS for the combination of lenvatinib plus pembrolizumab compared with placebo plus pembrolizumab. This futility analysis was requested at a previous eDMC meeting and conducted as described in the sSAP. Based upon these data and the recommendation of the eDMC, Amendment 007-06 was implemented to unblind the study and remove lenvatinib and matching placebo from the treatment arms. The prespecified interim and final analyses of the study described in the statistical analysis plan (SAP) will not be performed. Selected analyses of safety and ePRO endpoints will be performed at the end of the study; there will be no further analyses of efficacy endpoints.**

This section outlines the statistical analysis strategy and procedures for the study. **As of Amendment 007-06, the study has been unblinded.** Changes made to primary and/or key secondary hypotheses, or the statistical methods related to those hypotheses, that occurred prior to study unblinding were documented in previous protocol amendment(s) (consistent with International Council for Harmonisation [ICH] of Technical Requirements for Pharmaceuticals for Human Use Guideline E9). Changes to exploratory or other nonconfirmatory analyses made after the protocol has been finalized, but before unblinding/final database lock, will be documented in a supplemental statistical analysis plan (sSAP) and referenced in the clinical study report (CSR) for the study. Post hoc exploratory analyses will be clearly identified in the CSR. Separate analysis plans (ie, separate documents from the sSAP) will be developed to detail PK and biomarker analyses. The ePRO analysis plan will be included in the sSAP.

### 9.1 Statistical Analysis Plan Summary

Key elements of the SAP are summarized below. The comprehensive plan is provided in Sections 9.2 through 9.12. **As of Amendment 007-06, the prespecified interim and final analyses of the study described in SAP will not be performed. Selected analyses of safety and ePRO endpoints will be performed at the end of the study; there will be no further analyses of efficacy endpoints. The SAP summary has been updated accordingly.**

Study Design Overview	Phase 3 study of pembrolizumab plus lenvatinib vs pembrolizumab plus placebo for 1L treatment of metastatic NSCLC in participants whose tumors express PD-L1 (TPS $\geq$ 1%)
Treatment Assignment	Approximately 620 participants will be randomized in a 1:1 ratio between 2 treatment arms: (1) pembrolizumab + lenvatinib and (2) pembrolizumab + placebo. Stratification factors are as follows: 

Geographic region (East Asia vs non-East Asia)

ECOG PS (0 vs 1)

TPS (1%-49% vs <math>\geq</math>50%)

 As of Amendment 007-06, the study is unblinded and all ongoing participants will continue treatment with open-label pembrolizumab monotherapy.

Analysis Populations	Efficacy: Intention-to-Treat (ITT) Safety: All Participants as Treated (APaT)
Primary Endpoints	
 
• PFS per RECIST 1.1 based on BICR
 
• OS
 

Secondary Endpoints	
 
• OR per RECIST 1.1 based on BICR
 
• Safety and tolerability
 
• Change from baseline in Global health status/QoL, cough, chest pain, dyspnea and physical functioning scores
 
• Time to True Deterioration (TTD) in global health status/QoL, cough, chest pain, dyspnea, and physical functioning
 
• TTD in the composite endpoint of cough, chest pain, or dyspnea items
 

Statistical Methods for Key Efficacy Analyses	
As of Amendment 007-06, the prespecified interim and final analyses of the study will not be performed. There will be no further analyses of efficacy endpoints.
 
The primary hypotheses will be evaluated by comparing pembrolizumab + lenvatinib to pembrolizumab + placebo in PFS and OS using a stratified log-rank test and in ORR using the stratified Miettinen and Nurminen method [Miettinen, O. and Nurminen, M. 1985]. The HR will be estimated using a stratified Cox regression model. Event rates over time will be estimated within each treatment group using the Kaplan-Meier method. The difference in ORR will be estimated using the stratified Miettinen and Nurminen method with strata weighting by sample size.

Statistical Methods for Key Safety Analyses	The analysis of safety results will follow a tiered approach. The tiers differ with respect to the analyses that will be performed. There are no events of interest that warrant elevation to Tier 1 events in this study. Tier 2 parameters will be assessed via point estimates with 95% CIs provided for between-group comparisons; only point estimates by treatment group are provided for Tier 3 safety parameters. The 95% CIs for the between-treatment differences in percentages will be provided using the Miettinen and Nurminen method.
Interim Analyses	As of Amendment 007-06, no interim analyses of the study will be performed.
Multiplicity	As of Amendment 007-06, no interim or final analyses of the study will be performed.
Sample Size and Power	
As of Amendment 007-06, no interim or final analyses of the study will be performed.
 
The planned sample size is approximately 620 participants. For PFS, based on 416 events, the study has 86.5% power to detect a HR of 0.7 (pembrolizumab + lenvatinib vs pembrolizumab + placebo) at <math>\alpha=0.55\%</math> (1-sided). For OS, based on 388 events, the study has 90% power to detect a HR of 0.71 (pembrolizumab + lenvatinib vs pembrolizumab + placebo) at <math>\alpha=1.95\%</math> (1-sided).

China Extension Study	
As of Amendment 007-06, enrollment in the Extension Study in China has been stopped.
 
China participants randomized during the global study phase will be included in all global study analyses (efficacy and safety). China participants randomized during the China extension phase will be excluded from all global study analyses. China participants randomized during global and extension phases will both be included in any China-specific analyses.

## 9.2 Responsibility for Analyses/In-house Blinding

**Note: As of Amendment 007-06, the study is unblinded to the Sponsor, the investigational sites, and the participants. This section has been updated accordingly.**

The statistical analysis of the data obtained from this study will be the responsibility of the Clinical Biostatistics department of the Sponsor.

This study was conducted as a double-blind study under in-house blinding procedures until after the eDMC recommended study unblinding.

The Sponsor generated the randomized allocation schedule(s) for study intervention assignment. Blinding issues related to the planned interim analyses are described in Section 9.7, but are no longer applicable as of Amendment 007-06.

### Extension Study in China

For all participants in China, including participants randomized in the global study and the extension study, statistician(s)/programmers were blinded to participant level treatment randomization and this information had been clearly documented.

## 9.3 Hypotheses/Estimation

Objectives and hypotheses of the study are stated in Section 3.

## 9.4 Analysis Endpoints

Efficacy and safety endpoints that will be evaluated for within- and/or between-treatment differences are listed below.

### 9.4.1 Efficacy Endpoints

#### 9.4.1.1 Primary Endpoints

**PFS:** the time from randomization to the first documented PD per RECIST 1.1, adjusted to follow a maximum of 10 target lesions and a maximum of 5 target lesions per organ, based on BICR or death due to any cause, whichever occurs first. See Section 9.6.1 for the definition of censoring.

**OS:** the time from randomization to death due to any cause.

#### 9.4.1.2 Secondary Endpoints

**OR:** a confirmed CR or PR per RECIST 1.1, adjusted to follow a maximum of 10 target lesions and a maximum of 5 target lesions per organ, based on BICR.

#### 9.4.1.3

CCI

#### 9.4.2 Safety Endpoints

Safety and tolerability will be assessed by clinical review of all relevant parameters including AEs, SAEs, fatal AEs, laboratory tests, and vital signs. Furthermore, specific events will be collected and designated as ECIs as described in Section 8.4.7.

#### 9.4.3 Patient-reported Outcome Endpoints

The following secondary PRO endpoints will be evaluated as described in Section 4.2.1.3 and analyzed as described in Section 9.6.3:

##### *Change from baseline in*

- Global Health Status/QoL scale (QLQ-C30 items 29-30)
- Single-item symptom scales: cough (QLQ-LC13 item 31), chest pain (QLQ-LC13 item 40), and dyspnea (QLQ-C30 item 8)
- Physical functioning scale (QLQ-C30 items 1-5)

##### *Time to true deterioration (TTD) in*

- Global Health Status/QoL scale (QLQ-C30 items 29-30)
- Single-item symptom scales: cough (QLQ-LC13 item 31), chest pain (QLQ-LC13 item 40), and dyspnea (QLQ-C30 item 8)
- Physical functioning scale (QLQ-C30 items 1-5)
- Composite symptom endpoint: cough (QLQ-LC13 item 31), chest pain (QLQ-LC13 item 40), or dyspnea (QLQ-C30 item 8)

The TTD in global health status/QoL, cough, chest pain, dyspnea, and physical functioning is defined as the time from baseline to the first onset of a 10 or more points deterioration from baseline with confirmation by the subsequent visit of a 10 or more points deterioration from baseline. The TTD in the composite endpoint of cough, chest pain, or dyspnea is defined as the time to first onset of 10 or more points deterioration from baseline in any one of 3 scale items with confirmation by the subsequent visit of 10 points or more deterioration from baseline in the same scale as the first onset. The EQ-5D-5L will be evaluated as an exploratory endpoint. These analyses and other supportive PRO analyses will be described in the sSAP.

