#### **4.2.1.3 Patient-reported Outcomes**

##### **NOTE: As of Amendment 007-06, ePRO data are no longer being collected.**

Symptomatic improvement is considered a clinical benefit and accepted by health authorities. As part of the analyses for this study, participants will provide information regarding their health-related quality of life (HRQoL) via the following assessment tools: European Organization for Research and Treatment of Cancer (EORTC) QLQ-C30, EORTC QLQ-LC13, and EuroQoL EQ-5D-5L questionnaires. The ePROs are not pure efficacy or safety endpoints because they are affected by both PD and treatment tolerability.

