### **8.2.2 Patient-reported Outcomes**

**NOTE: As of Amendment 007-06, PROs will no longer be collected. This section is no longer applicable.**

The EORTC QLQ-C30, EORTC QLQ-LC13, and EQ-5D-5L questionnaires will be administered by trained site personnel and completed electronically by participants in the following order: EORTC QLQ-C30, EORTC QLQ-LC13, and lastly EQ-5D-5L. The questionnaires should be administered before dosing at every cycle through Cycle 17, then every other cycle through Cycle 35 (eg, Cycles 1-17, 19, 21, 23, 25, 27, 29, 31, 33, and 35), at the Treatment Discontinuation Visit, and at the 30-day Safety Follow-up Visit.

If the Treatment Discontinuation Visit occurs 30 days from the last dose of study intervention, at the time of the mandatory Safety Follow-up Visit, the electronic patient-reported outcomes (ePROs) do not need to be repeated.

It is best practice and strongly recommended that the ePROs are administered to randomized participants before drug administration, AE evaluation, and disease status notification. If the participant does not complete the ePROs at a scheduled time point, the MISS\_MODE form must be completed to capture the reason the assessment was not performed.

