#### 9.6.1.1 Progression-free Survival

The nonparametric Kaplan-Meier method will be used to estimate the PFS curve in each treatment group. The hypotheses of treatment difference in PFS will be tested by the stratified log-rank test. A stratified Cox proportional hazard model with Efron's method of tie handling will be used to estimate the magnitude of the treatment difference (ie, HR) between the treatment arms. The HR and its 95% CI from the stratified Cox model with Efron's method of tie handling and with a single treatment covariate will be reported.

Since PD is assessed periodically, PD can occur any time in the time interval between the last assessment where PD was not documented and the assessment when PD is documented. For the primary analysis, for the participants who have PD, the true date of PD will be approximated by the date of the first assessment at which PD is objectively documented per RECIST 1.1 by the BICR vendor, regardless of discontinuation of study drug. Additional analyses will be performed for PFS per iRECIST.

To evaluate the robustness of the PFS endpoint per RECIST 1.1 via BICR by the imaging vendor, 1 primary and 2 sensitivity analyses with a different set of censoring rules will be performed. For the primary analysis, if the events (PD or death) are after more than 1 missed disease assessment, the data are censored at the last disease assessment before missing visits. Also, data after new anticancer therapy are censored at the last disease assessment before the initiation of new anticancer therapy. The first sensitivity analysis follows ITT principles (ie, PDs/deaths are counted as events regardless of missed study visits or initiation of new

anticancer therapy). The second sensitivity analysis considers discontinuation of treatment or initiation of an anticancer treatment after discontinuation of study-specified treatments, whichever occurs later, to be a PD event for participants without documented PD or death. If a participant meets multiple criteria for censoring, the censoring criterion that occurs earliest will be applied. The censoring rules for primary and sensitivity analyses are summarized in Table 8.

Table 8 Censoring Rules for Primary and Sensitivity Analyses of Progression-free Survival

Situation	Primary Analysis	Sensitivity Analysis 1	Sensitivity Analysis 2

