#### Time to Deterioration (TTD)

For the TTD endpoints defined in Section 9.4.3, the Kaplan-Meier method will be used to estimate the TTD curve for each treatment group. The estimate of median time to deterioration and its 95% CI will be obtained from the Kaplan-Meier estimates. The treatment difference in TTD will be assessed by the stratified log-rank test. A stratified Cox proportional hazard model with Efron's method of tie handling and with a single treatment covariate will be used to assess the magnitude of the treatment difference (ie, HR). The HR and its 95% CI will be reported. The same stratification factors used for the stratified PFS and OS analyses will be used as the stratification factors in both the stratified log-rank test and the stratified Cox model.

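### Does time to true deterioration need a written rule for a worsening first seen on the last questionnaire?

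*Combined protocol and SAP*

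**What the plan says.** Section 9.4.3 defines TTD for each single scale as "the time from baseline to the first onset of a 10 or more points deterioration from baseline with confirmation by the subsequent visit". For the composite symptom endpoint, the confirming drop must be in the scale that dropped first. Section 9.6.3 gives the methods: Kaplan-Meier curves, a stratified Cox model, and "The treatment difference in TTD will be assessed by the stratified log-rank test". It has no censoring table for TTD. PFS does have one (Table 8, "Censoring Rules for Primary and Sensitivity Analyses of Progression-free Survival"), and so does duration of response (Table 9).

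Under Section 8.2.2, forms were due at each cycle to Cycle 17, at alternate cycles to Cycle 35, and then "at the Treatment Discontinuation Visit, and at the 30-day Safety Follow-up Visit". When those last two visits fall together, one form serves for both.

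Three other statements bear on the point:

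- The opening of Section 9 assigns the ePRO analysis plan to the supplemental SAP (sSAP).
- The same section says that, after the futility stop, "Selected analyses of safety and ePRO endpoints will be performed at the end of the study". The note at Section 9.6 keeps the methods subsections for reference only.
- Section 9 also provides that "Post hoc exploratory analyses will be clearly identified in the CSR".

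**The concern.** Confirmation is part of the event. A drop of 10 or more points therefore goes uncounted when it first appears on the last form before death, on the 30-day form, on a combined discontinuation and 30-day form, or just before later forms are missed. Without another rule, that participant is censored.

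Censoring of this kind may be informative. Section 4.2.1.3 says of the ePROs that "they are affected by both PD and treatment tolerability", so the people who stop filling in forms may be those getting worse. Tolerability may also differ by arm: in the placebo-controlled lenvatinib study cited in Section 2.1 (24 mg daily, later-line disease), Grade 3 or 4 adverse events were 69% against 50%. If lost confirmation is both linked to deterioration and unequal between arms, the log-rank and Cox comparison favours the arm that loses more confirmations. A reader of the protocol alone could not tell whether this had happened. PFS and duration of response have explicit rules, so the silence on TTD looks like an oversight.

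**Working it through.** **No stated figure to reproduce.** The documents give no event count, power, alpha or completion rate for TTD. The one relevant design number is the control-arm PFS assumption in Section 9.9, a median of 5 months up to 6.5 months. It implies 1 − 2^(−6.5/5) = 1 − 0.406 = 0.594 with progression or death by 6.5 months. So many participants reach a point where forms may stop. But this is one arm only, says nothing about a difference between arms, and treatment past progression was allowed.

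**What is undecided.** Event status is settled: no confirmation, no event. Two details are open in the protocol: the censoring date, and whether the subsequent visit means the next scheduled or the next completed form. An analyst would ordinarily censor at the last completed form.

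**How large could the effect be?** A simulation with no true difference used the Section 8.2.2 schedule, with 300,000 per arm, six seeds and Cox with Efron ties. All rates are assumptions:

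- onset of deterioration 5% per cycle in both arms, 30% of drops transient
- 10% of on-treatment forms missed
- death 0.5% per cycle except where stated
- discontinuation and 30-day visits coinciding in 20%
- entry over 21.7 months, ePRO stop at month 30

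Stopping was 6% against 4% per cycle in the unequal-stopping rows; in the linked rows these rates were multiplied by six while deteriorated. The hazard ratio is the arm losing more against the other.

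| Setting | As defined | Last unconfirmed drop counted as event |
|---|---|---|
| Linked loss, equal in both arms | 1.00 | 1.00 |
| Unequal stopping, unrelated to deterioration | 1.00 | 1.02 |
| Linked; discontinuation/30-day forms 80%/60% complete | 0.98 | 1.03 |
| Linked; forms 50%/30% complete | 0.94 | 1.03 |
| Linked; neither form ever completed | 0.82 | 1.03 |
| Deaths 1.5% vs 0.75% per cycle, four times likelier while deteriorated | 0.94 | 0.98 |

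The Monte Carlo error of the hazard ratios as defined is about 0.003. Unconfirmed last drops per 310 in the three linked, unequal rows are 15 vs 12, 26 vs 22 and 50 vs 42. Removing the ePRO stop left the hazard ratio unchanged.

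**Against sampling error.** With about 90 and 107 events in the two arms, the standard error of the log hazard ratio is √(1/90 + 1/107) = √0.02046 = 0.143. The shifts are:

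- ln 0.98 = −0.020, or 0.14 standard errors
- ln 0.94 = −0.062, or 0.43 standard errors
- ln 0.82 = −0.198, or 1.39 standard errors

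Only the setting with no post-treatment forms exceeds one standard error, and Section 8.2.2 scheduled both forms.

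**Would the added analysis be better?** With unrelated stopping it moves from 1.00 to 1.02. With 80%/60% completion it moves from 0.98 to 1.03, and ln 1.03 = 0.030 is further from zero than −0.020. It is closer to 1 in the heavier-loss rows and the unequal-death row. If half of all drops are transient and no post-treatment forms exist, it reaches 1.08. It exchanges one bias for another.

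**The case for a change.** The strongest counter-case is that linked, unequal loss can do more harm than the table suggests. A second simulation used 310 per arm, no true difference, a median of 40 weeks to deterioration and on-treatment forms only. It set directly the share of deteriorating participants who give no later form. With 20%, 30% and 40% in one arm against 10% in the other, the hazard ratio was 0.88, 0.80 and 0.64; counting the last drop as an event restored it to 1.00, 1.01 and 0.99. The extra run and a count table would be cheap, use existing data, and could be labelled post hoc.

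The mechanism and its direction stand. The size does not carry over. That simulation leaves out the two post-treatment forms that exist to catch such cases and imposes the imbalance instead of deriving it. It rests on 100 runs per setting, and its equal-loss setting returned 1.03, so it carries simulation error of a few hundredths. Nothing in the documents shows that loss was unequal or linked to deterioration.

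It also stands that the sSAP was not available to check. But silence in Section 9.6.3 is what one expects when Section 9 assigns the ePRO plan to another document. Tables 8 and 9 belong to efficacy endpoints whose rules were kept in the protocol.

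**Conclusion.** No change to the plan follows. The gap is delegated detail that an analyst can fill sensibly: an unconfirmed drop is already a non-event, and the rest is a censoring convention that belongs in the sSAP.

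Little is at stake. TTD is secondary with no stated alpha, the trial stopped for OS futility, and TTD may not be among the selected ePRO analyses. Under the assumed rates, and with some scheduled post-treatment forms completed, the distortion is a hazard ratio of 0.98 or 0.94 against a standard error of about 0.14. A value such as 0.82 requires that those forms were never returned, as well as stopping that is both linked to deterioration and unequal.

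Writing a new main-analysis rule now, after unblinding, would be less credible than relying on the sSAP. The alternative analysis is further from the null in the milder settings. If TTD is reported, counts of unconfirmed last drops by arm, with reasons, would help the reader. That is an optional reporting matter, and the existing provision for labelling post hoc work covers an analysis that counts those drops as events. The conclusion would weaken if such counts proved markedly unequal.
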